### 9.4 Safety

To assess the safety and tolerability of opaganib administered orally at 500 mg Q 12 hours, for up to 14 days, in patients with severe COVID-19 pneumonia.

## 10 STUDY POPULATION

The study population will consist of patients diagnosed with COVID-19 infection that is defined as severe based on eligibility criteria to align with current region-specific diagnostic guidance. Specifically, patients will at minimum have pneumonia secondary to SARS-CoV-2, radiographic evidence of pneumonia on chest X-ray or CT scan, and require supplemental oxygen by high flow oxygen via nasal cannula or positive pressure ventilation or is receiving oxygen via non-rebreather or reservoir face mask, capable of delivering high concentrations of oxygen. The patients must be hospitalized at least during screening and at baseline (Day 1).

## 11 ELIGIBILITY CRITERIA

### 11.1 Inclusion Criteria

- 1) Adult male or female  $\geq 18$  to  $\leq 80$  years of age
- 2) Proven COVID-19 infection per RT-PCR assay of a pharyngeal sample (nasopharyngeal or oropharyngeal) AND pneumonia defined as radiographic opacities on chest X-ray or CT scan that diagnosed COVID-19 pneumonia. Pharyngeal samples collected either at screening or within 7-days prior to screening for the same ongoing COVID-19 pneumonia illness are acceptable.
- 3) The patient requires, at baseline, high flow supplemental oxygen or positive pressure or is receiving oxygen via face mask, such as a non-rebreather or reservoir mask, capable of delivering high concentrations of oxygen.
- 4) Male participants with female partners of child-bearing potential agree to one of the following methods of contraception during the treatment period and for at least 1 month after the last dose of study drug:
  - Abstinence from penile-vaginal intercourse and agree to remain abstinent.
  - Male condom, with female partner using a highly effective contraceptive method. (For further details regarding highly effective contraceptive methods refer to Section 11.3).

In addition, male participants must refrain from donating sperm for the duration of the study and for 1 month after last dose of study drug.

Male participants with a pregnant or breastfeeding partner must agree to remain abstinent from penile-vaginal intercourse or use a male condom during each episode of penile penetration for at least 1 month after the last dose of study drug

Female participants:

A female participant is eligible to participate if she is:

- a) not pregnant
- b) not breastfeeding
- c) not a woman of child-bearing potential (WOCBP, as defined in Section 11.3)
- d) a WOCBP who agrees to use a highly effective method of contraception consistently and correctly during the treatment period and for at least 1 month after the last dose of study drug (refer to Section 11.3 for further details).

- 5) The patient or legal representative has signed a written informed consent approved by the IRB/Ethics Committee

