## 12 STUDY DESIGN

### 12.1 Overall Investigation Plan

This is a phase 2/3 multi-center randomized, double-blind, parallel arm, placebo-controlled study, with an adaptive design that will utilize a futility assessment. The study is planned to be performed worldwide in approximately up to 80 clinical sites.

After informed consent is obtained, patients will enter a screening phase for no more than 3 days, to determine eligibility. Approximately 464 eligible patients will be randomized and receive either opaganib added to standard of care, or matching placebo added to standard of care, in a randomization ratio of 1:1. Treatment assignments will remain blinded to the patient, investigator and hospital staff, as well as the sponsor.

Study participants will receive either opaganib 2 x 250 mg capsules (500 mg) every 12 hours, or matching placebo, in addition to standard of care (pharmacological as defined above and/or supportive) at any given institution. Study drug will be administered every day for 14 days (Day 1 to Day 14).

All participants will be followed up for 42 days after their first dose of study drug. The maximum duration of study participation will be up to 45 days (including up to 3 days screening; up to 14 days of double-blind treatment and completion of study at Day 42).

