### 15.2 Secondary

- 1) The percentage of patients with  $\geq 2$  category improvement on the WHO Ordinal Scale for Clinical Improvement by Day 14 for the opaganib arm as compared to the placebo arm
- 2) Time to recovery as defined by improvement to a score of 3 or less on the WHO Ordinal Scale for Clinical Improvement for the opaganib arm as compared to the placebo arm
- 3) Time to low oxygen flow via nasal cannula e.g. from high oxygen flow via nasal cannula or positive pressure ventilation at baseline
- 4) The time to discharge from the hospital for the opaganib arm as compared to the placebo arm
- 5) The percentage of patients requiring intubation and mechanical ventilation by day 42 for the opaganib arm as compared to the placebo arm
- 6) The time to two consecutive negative swabs for SARS-CoV-2 by PCR, at least 24 hours apart for the opaganib arm as compared to the placebo arm
- 7) The percentage of patients with at least two consecutive negative swabs for SARS-CoV-2 by PCR at Day 14 for the opaganib arm as compared to the placebo arm
- 8) The percentage of patients with at least one measurement of fever at baseline (defined as temperature  $>38.0$  C [100.4 F]), who are afebrile (defined as temperature  $<37.2$  C [99 F]) at Day 14 for the opaganib arm as compared to the placebo arm
- 9) Mortality due to any cause at Days 28 and 42 after baseline for the opaganib arm as compared to the placebo arm

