### 19.3 Populations for Analysis

The primary analysis will be based on the modified Intent to treat population (mITT), which consists of all patients that were randomized and treated with at least one dose of study drug and who met entry criteria #3 (The patient requires, prior to first dose of study drug, high flow supplemental oxygen or positive pressure ventilation, or is receiving oxygen via a non-rebreather or reservoir mask, capable of delivering high concentrations of oxygen. Patients who require mechanical ventilation or no longer

require supplemental oxygen prior to receiving the first dose of study drug will not be included in the mITT analysis set.

The primary analysis will also be analyzed using a Per-Protocol (PP) population that will be further defined in the SAP and the Intention-to-treat (ITT) population who consists of all randomized patients. In all efficacy analyses, treatment group will be assigned per randomization assignment.

Safety analyses will be based on the safety analysis set, which consists of all patients who received at least one dose of study drug and analyzed based on the actual treatment the subject received.

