Time to event endpoints will be calculated as the number of days from study day 1 until the event of interest or last valid observation time, whichever occurs first (within endpoint timeframe). A patient for whom event of interest will not be observed will be regarded as right censored. Unless otherwise specified in the SAP, the time frame for primary analysis of these endpoints is from Day 1 until Day 14. Time to discharge from hospital will be using end of Day 14 of treatment as end-of-time frame. When event of interest is of Improvement/Recovery type (such as time to recovery), death within the timeframe for each endpoint, will be addressed corresponding to the highest unfavorable possible outcome for the endpoint, which is censoring at the end of time frame.

Time to event endpoints will be compared using the stratified Log-rank test and the stratified Cox proportional hazards regression model will be used to estimate the hazard ratio (HR) along with 95% confidence interval, comparing opaganib versus control group. Kaplan-Meier plot by treatment arm will be presented and cumulative incidence of events of interest will be estimated along with 95% confidence interval for each group at several time points within timeframe.

Mortality endpoints will be defined per subject as a binary variables indicating if a subject had died by target times (28 and 42) days from first dose date. These binary endpoints will be analyzed using the same methods specified for the binary endpoints above. To note, in case of early discontinuation of follow-up, time to event analysis to derive the -days mortality rate will be applied, censoring such subjects at their last valid observation date.

All secondary endpoints analyses will be based on mITT population and PP population and undergo the same sensitivity analyses as the primary analysis, as applicable.

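### The two PCR-clearance endpoints (secondary 6 and 7) are analysed in all mITT patients with no requirement to be PCR-positive before the first dose, which attenuates the estimated antiviral effect and generally costs power

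*Protocol*

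**What the plan says.** Inclusion criterion 2 (Protocol Section 11.1) requires a positive RT-PCR on a sample taken at screening and adds that samples "within 7-days prior to screening for the same ongoing COVID-19 pneumonia illness are acceptable". Section 12.1 adds that "patients will enter a screening phase for no more than 3 days, to determine eligibility".

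The mITT (Section 19.3) consists of "all patients that were randomized and treated with at least one dose of study drug and who met entry criteria #3". Criterion 3 concerns oxygen support, and the definition has no PCR condition. It does remove patients who no longer need oxygen before the first dose.

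The two viral endpoints in Section 15.2 are "The time to two consecutive negative swabs for SARS-CoV-2 by PCR, at least 24 hours apart" (endpoint 6) and "The percentage of patients with at least two consecutive negative swabs for SARS-CoV-2 by PCR at Day 14" (endpoint 7). Neither mentions baseline PCR status. Endpoint 8, in the same list, counts only patients with fever at baseline.

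Section 19.5 states: "All secondary endpoints analyses will be based on mITT population and PP population". It counts time to event from Day 1. Table 1 marks a pharyngeal sample at screening and on Day 1, and its footnote 5 lets testing stop once two negatives are confirmed.

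**The concern.** A patient can be enrolled on a swab up to 10 days old, be PCR-negative before the first dose, and stay in the denominator. If the next swab confirms the negative, that patient meets endpoint 6 within days of starting treatment. Because testing may then stop, the patient will normally count as a success for endpoint 7 as well. This happens in either arm, and such patients tell us little about whether the drug speeds clearance.

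The protocol applies the opposite logic elsewhere: endpoint 8 requires the condition at baseline, and the mITT drops patients who have already come off oxygen. The PP set would not remove the baseline-negative patients, because an older swab is permitted. None of the sensitivity analyses listed in Section 19.4 conditions on PCR status.

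At stake are the size of the reported antiviral effect, which is central to the drug's rationale, and the power of these two tests.

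**Working it through.** **The plan's own figure.** Section 19.1 assumes 40% versus 55%, two-sided 0.05, 90% power and a chi-square test, and gives 464 patients (232 per arm). The pooled-variance formula without continuity correction gives 231 per arm, or 462, and power of 90.1% at 232 per arm. The stated figure reproduces. It concerns the primary endpoint; the protocol gives no power for the viral endpoints.

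**Age of the swab.** 7 days before screening + 3 days of screening = 10 days at most.

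**Inputs for the dilution.**
- q, the share PCR-negative before the first dose: not in the documents; 5% to 30% is assumed.
- Clearance by Day 14 in the remainder: 40% versus 55%, borrowed from the primary endpoint for illustration only.
- n = 232 per arm for all mITT, taking every randomised patient as mITT. The baseline-positive set has 232(1 − q), rounded.

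**Formulas.** If a fraction c of the already-negative patients confirms, an arm's rate is qc + (1 − q)p. The difference between arms is (1 − q)(0.55 − 0.40) + q(c_T − c_C), where c_T and c_C are the confirming fractions on opaganib and placebo. When all confirm, or the same fraction confirms in each arm, the second term is zero and the 15 points shrink by the factor (1 − q).

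Power = Φ{[d − 1.96 √(2 p̄(1 − p̄)/n)] / √([p_C(1 − p_C) + p_T(1 − p_T)]/n)}.

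Example, q = 20%, all confirm: p_C = 0.2 + 0.8 × 0.40 = 0.52, p_T = 0.2 + 0.8 × 0.55 = 0.64, d = 0.12, p̄ = 0.58. The two standard errors are 0.0458 and 0.0455, so power = Φ[(0.12 − 0.0898)/0.0455] = 74.7%. In baseline positives n = 186, d = 0.15, and power = 82.8%.

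**Endpoint 7, all already-negative patients confirm:**

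| q | Difference, all mITT | Power, all mITT | n per arm, baseline positives | Power, baseline positives |
|---|---|---|---|---|
| 0% | 15.0 | 90.1% | 232 | 90.1% |
| 5% | 14.3 | 86.9% | 220 | 88.6% |
| 10% | 13.5 | 83.2% | 209 | 86.9% |
| 20% | 12.0 | 74.7% | 186 | 82.8% |
| 30% | 10.5 | 65.1% | 162 | 77.4% |

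The ranking is the same with 30% versus 45% and with 60% versus 75%. At q = 20% those give 73.5% against 85.1%, and 84.0% against 87.4%.

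**If treatment also affects confirmation.** With 80% of already-negative placebo patients confirming against 90% on opaganib, the difference in all mITT is 14.5, 14.0 and 13.5 points at q = 10%, 20% and 30%. Power is 88.0%, 86.0% and 84.2%, which is above the baseline-positive set. With 85% against 90%, power is 85.7%, 80.6% and 75.1%, about 1 to 2.5 points below it.

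**Endpoint 6.** This was a simulated unstratified log-rank test with 2,000 runs, exponential clearance giving 40% versus 55% by Day 14, swabs every 3 days, and already-negative patients confirmed on Day 2. At q = 10%, 20% and 30%:
- the mean hazard ratio in all mITT falls from 1.62 (at q = 0) to 1.45, 1.37 and 1.30;
- power in all mITT is 74.5%, 63.1% and 48.5%;
- power in baseline positives is 83.3%, 79.7% and 73.9% (87.9% at q = 0).

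**The case against.** The protocol sends full detail to a SAP that is not shown, and endpoint 8 has a restricted denominator although it falls under the same mITT sentence. On that view, basing an analysis on the mITT leaves room for an evaluable subset. This stands only in part. Endpoint 8 states its restriction in its own definition and endpoints 6 and 7 do not; the population sentence in Section 19.5 carries no deferral to the SAP, although neighbouring rules do.

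A reader might infer that no treatment effect is possible in a patient negative on Day 1. The documents do not support that. The endpoint needs two negatives at least 24 hours apart, the confirming swab comes after dosing, and it can be positive. The main table is therefore a limiting case. If treatment affects confirmation, the advantage of the restricted set shrinks and can reverse.

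The size is uncertain. No share already negative is given. Section 7.1 cites a median shedding time of 20 days (interquartile range 17 to 24), which suggests that the share may be small, and Section 12.2 asks for the shortest possible interval from screening to first treatment. Ten days is the outer limit. Against this, eligibility sets no limit on time since symptom onset, so a small share cannot be assumed either.

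A reader might also infer that the diluted tests stand sixth and seventh in the hierarchy and would block fever and mortality. Section 19.7 describes sequential testing of the secondary endpoints but does not say that it follows the listed order, so that consequence is not established.

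**Conclusion.** The point holds as a matter of analysis choice. As written, endpoints 6 and 7 include patients who may already be PCR-negative before treatment. Those who confirm count as clearances in either arm, which pulls the estimated difference towards zero and generally lowers power. Under the limiting assumption that all confirm, the loss of power relative to baseline positives is under 2 points at q = 5%, under 4 at 10%, about 8 at 20% and about 12 at 30% for endpoint 7. It is larger in the simulation of endpoint 6. These sizes rest on an assumed q and on borrowed clearance rates.

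This should not be read as a false-positive risk. Randomisation keeps the comparison valid under the null hypothesis, so type I error is not inflated, and the primary endpoint and the 464 are untouched. The change is a cheap improvement to two secondary endpoints; nothing here invalidates a result.

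**What to change.** For endpoints 6 and 7, define the main analysis set as mITT patients whose last swab collected before the first dose is PCR-positive, and report all mITT patients as supportive. State in Table 1 or Section 14.1 that the Day 1 swab is taken before dosing. At present no text says so, whereas the baseline oxygen reading and the Day 1 ECG are expressly tied to the time before the first dose. Without that sentence a Day 1 result could be post-treatment, and a subset built on it would not be fixed before treatment.

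The cost is wording in the protocol and SAP plus one timing instruction to sites; the swab is already scheduled. The downside is fewer patients in the main analysis of these two endpoints, for example 186 instead of 232 per arm if 20% are already negative.

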### 11.2 Exclusion Criteria

- 1) Any co-morbidity that may add risk to the treatment in the judgment of the investigator, particularly patients with known cardiac conditions, and serious neuropsychiatric conditions such as psychosis or major depression.
- 2) Requiring intubation and mechanical ventilation at baseline

- 3) has a 'Do Not Intubate' and/or 'Do Not Resuscitate' order in place
- 4) Oxygen saturation >95% on room air
- 5) Any preexisting respiratory condition that requires intermittent or continuous ambulatory oxygen prior to hospitalization
- 6) Patient is, in the investigator's clinical judgement, unlikely to survive >72 hours
- 7) Pregnant (positive serum or urine test within 3 days prior to randomization) or nursing women
- 8) Unwillingness or inability to comply with procedures required in this protocol.
- 9) Corrected QT (QTc) interval on electrocardiogram (ECG) >470 ms for females or >450 ms for males, calculated using Friedericia's formula (QTcF)
- 10) AST (SGOT) or ALT (SGPT) > 2.0 x upper limit of normal (ULN)
- 11) Total bilirubin >1.5 x ULN (except where bilirubin increase is due to Gilbert's Syndrome)
- 12) Serum creatinine >2.0 X ULN
- 13) Absolute neutrophil count <1000 cells/mm^3
- 14) Platelet count <75,000/mm^3
- 15) Hemoglobin <8.0 g/dL
- 16) Medications that are sensitive substrates, or substrates with a narrow therapeutic range, for CYP1A2, CYP2B6, CYP2C8, CYP2C9, CYP2C19 CYP2D6 , CYP3A4, P-gP, BCRP and OATP1B1 should be avoided with opaganib. Please see Appendix 2
- 17) Moderate or strong inhibitors of CYP1A2, CYP3A4, CYP2D6 or P-gP or moderate to strong inducers of CYP3A4 and CYP1A2 are prohibited. Please see Appendix 2
- 18) Currently taking warfarin, apixaban, argatroban or rivaroxaban due to drug-drug interaction based on CYP450 metabolism. For washout periods, refer to Section 13.1.4.
- 19) Current drug or alcohol abuse
- 20) Currently participating in a clinical study assessing pharmacological treatments, including anti-viral studies.
- 21) Treatment with any medication that causes QT prolongation within seven days, or 5 half-lives, whichever is longest, prior to initiation of study drug, or intention to use them throughout the study, including but not limited to: amiodarone, amitriptyline, citalopram dose greater than 20 mg/day, dihydroergotamine, disopyramide, dofetilide, dronedarone, ergotamine, ibutilide, ondansetron or other 5-HT3 receptor antagonists, pimozide, procainamide, quinidine, quinine, quinolone, ranolazine, risperidone, sotalol and tolteridine. Investigators are directed to the following up-to-date web site listing QT-prolonging drugs:  
<https://www.crediblemeds.org/index.php/drugsearch>

### **11.3 Women of Childbearing Potential Definition**

For the purpose of this protocol, a woman is considered of childbearing potential (WOCBP), i.e. fertile, following menarche and until becoming post-menopausal unless permanently sterile. Permanent sterilisation methods include hysterectomy, bilateral salpingectomy, bilateral tubal ligation and bilateral oophorectomy.

A postmenopausal state is defined as no menses for 12 months without an alternative medical cause. A high follicle stimulating hormone (FSH) level in the postmenopausal range may be used to confirm a post-menopausal state in women not using hormonal contraception or

hormonal replacement therapy. However, in the absence of 12 months of amenorrhea, a single FSH measurement is insufficient.

Highly effective contraceptive measures for WOCBP include:

- a. intrauterine device
- b. vasectomized partner (provided that the male vasectomized partner is the sole sexual partner of the WOCBP study participant and that the vasectomized partner has obtained medical assessment of surgical success for the procedure)
- c. and/or sexual abstinence.
- d. If combined (estrogen and progestogen containing) hormonal contraception (oral, intravaginal, transdermal) or progestogen-only hormonal contraception (oral, injectable, implantable), intrauterine hormone-releasing system associated with inhibition of ovulation is utilized then a back-up method of highly effective birth control is required, for example condom plus spermicide, cervical cap plus spermicide.

Periodic abstinence (calendar, symptothermal, post ovulation methods), withdrawal (coitus interruptus), spermicides only, and lactational amenorrhea method (LAM) are not acceptable methods.

## 12 STUDY DESIGN

### 12.1 Overall Investigation Plan

This is a phase 2/3 multi-center randomized, double-blind, parallel arm, placebo-controlled study, with an adaptive design that will utilize a futility assessment. The study is planned to be performed worldwide in approximately up to 80 clinical sites.

After informed consent is obtained, patients will enter a screening phase for no more than 3 days, to determine eligibility. Approximately 464 eligible patients will be randomized and receive either opaganib added to standard of care, or matching placebo added to standard of care, in a randomization ratio of 1:1. Treatment assignments will remain blinded to the patient, investigator and hospital staff, as well as the sponsor.

Study participants will receive either opaganib 2 x 250 mg capsules (500 mg) every 12 hours, or matching placebo, in addition to standard of care (pharmacological as defined above and/or supportive) at any given institution. Study drug will be administered every day for 14 days (Day 1 to Day 14).

All participants will be followed up for 42 days after their first dose of study drug. The maximum duration of study participation will be up to 45 days (including up to 3 days screening; up to 14 days of double-blind treatment and completion of study at Day 42).

### 12.2 Randomization Strategy

Randomization will be done centrally, using pre-determined schedule, and will assign subjects in a 1:1 ratio to opaganib added to standard of care or matching placebo added to standard of care.

In order to ensure balance of standard treatment regimens in both treatment arms as well as with regard to patient risk status, randomization will be determined according to two stratification factors:

- a) Whether SoC treatment has established efficacy (yes versus no). The proven effective therapies for the purpose of this protocol will be adjusted as new data emerges and will be documented in a stand-alone document entitled Approved COVID-19 Therapies which will be updated and shared with study personnel regularly.
- b) Patients will further be stratified based on meeting three or more high risk clinical parameters for COVID-19 outcomes at baseline (yes or no).

The parameters are: 1) age at screening,  $\geq 60$  years of age, (yes or no); 2) male, (yes or no); 3) HbA1c at screening,  $\geq 6.5$  and/or on active treatment with insulin or oral hypoglycemics (yes or no); 4) hypoxemia without commensurate increased work of breathing (defined as increased respiratory rate, nasal flaring and/or increase use of respiratory muscles including the diaphragm [yes or no]; 5) known underlying chronic lung disease (yes or no); 6) known cardiovascular disease or hypertension (yes or no); 7) BMI  $\geq 28.0$  kg/m^2 (yes or no); 8) known renal disease (yes or no).

Should clinical or laboratory changes occur between screening and randomization-or between randomization and first dose of study drug- that affect patient eligibility, the patient should not be

treated. In order to avoid this situation, screening, randomization and first treatment should preferably be accomplished in the shortest time interval possible.

